1. REPORTING & ANALYSIS PLAN SYNOPSIS

Overview	Key Elements of the RAP
Purpose	This RAP describes all the planned analyses and outputs required for the end of study Synoptic Report for study 201023.
Protocol	This RAP is based on the original protocol [(Dated: 12/Jul/2016) of study 201023(GSK Document No: 2016N281688_00] and eCRF Version 1
Primary Objective	To assess the efficacy of treatment with IV DNX twice daily given with oral oseltamivir compared to oral oseltamivir twice daily on time to clinical response (TTCR)
Primary Endpoint	Time to Clinical Response (composite) • Hospital discharge OR • Normalization of: - Temperature; and - Oxygen status; and - Respiratory status/Heart Rate/SBP(normalization of 2 out of these 3 parameters)
Study Design	Phase 2, randomized, double-blind (for IV DNX), placebo-controlled (for IV DNX) 3-arm study in adults to determine the efficacy and safety of IV DNX when coadministered (in all groups) with standard of care antiviral treatment (openlabel oral 75 mg OSV) for patients hospitalized with influenza.
	 Enrolled Subjects will be randomized 2:2:1 to 15 mg FBE IV DNX, 50 mg FBE IV DNX, or matching placebo. All subjects will also receive open-label oral OSV, twice daily (given as standard of care).
	Study treatment duration will be for up to 5 days. The investigator may elect to continue treatment with standard of care (OSV) after 5 days of study treatment.
	The sample size of 300 was selected based on simulations to achieve at least 80% overall power under assumption of HR =1.5 for 50 mg of DNX FBE and HR =1.2 for 15 mg of DNX FBE and keep type I error less than 10% under no-effect assumption. The study was terminated early after 10 subjects were enrolled.
	An Independent Data Monitoring Committee (IDMC) will perform monitoring and reviews of available safety and efficacy data.
	All decisions regarding final analysis, as defined in this RAP document, will be made prior to unblinding of the study data.
Planned Analyses	The final analysis will occur when both accrual and follow-up are complete for all subjects.
Primary Analysis Populations	• 'Influenza Positive Population' (IPP) comprises of all subjects in the ITT-E population with influenza infection (positive influenza PCR or culture at any timepoint) confirmed by central lab testing.

Overview	Key Elements of the RAP
Hypothesis	No formal hypotheses will be tested and only descriptive summaries will be created for the final analysis.
Primary Analyses Secondary Analyses	 Kaplan-Meier estimates for the median of TTCR for each treatment group and 95% confidence interval (CI) will be provided. Median, and 95% CI for time to respiratory response will be provided. Proportion of subjects with clinical response, and improved respiratory status will be summarized. Frequency of antibiotic use Frequency of adverse events (AEs) and serious adverse events (SAEs) Frequency of adverse events of special interest (AESIs) Change from baseline in clinical laboratory evaluations Summarize standard pharmacokinetic parameters for IV DNX (i.e. AUC, Cmax, Cavg).
Exploratory Analyses	 Change in quantitative influenza viral load over time and change from baseline measured from nasopharyngeal swab samples as determined by qRT-PCR and quantitative virus culture (qVC) Percentage of subjects with no detectable influenza viral RNA by qRT-PCR and qVC.
	Percentage of subjects with co-infected viruses by multiplex RT PCR.
	• Percentage by type of co-infected viruses by multiplex RT PCR.
	• Quantitative and qualitative changes in exploratory biomarkers (may include but are not limited to: IL-8, procalcitonin, respiratory neutrophil cell counts, neutrophil elastase, and myeloperoxidase).
	PK exposure for DNX and pharmacodynamic parameters.
	• FLU PRO questionnaire
	Activities of daily living (Katz ADL Score)

2. SUMMARY OF KEY PROTOCOL INFORMATION

2.1. Changes to the Protocol Defined Statistical Analysis Plan

Given that the study has been terminated early and only 10 subjects have been enrolled, no formal hypothesis testing will be performed for the study. All analyses will be descriptive and not intended for making definitive conclusions. Only a selected set of originally planned analyses will be performed and all data will be listed.

2.2. Study Objective(s) and Endpoint(s)

	Objectives	Endpoints
Pri	mary	•
•	To assess the efficacy of treatment with IV DNX twice daily given with oral oseltamivir compared to oral oseltamivir twice daily on time to clinical response (TTCR)	Time to Clinical Response (composite) Hospital discharge OR Normalization of: - Temperature; and - Oxygen status; and - Respiratory status/Heart Rate/SBP(normalization of 2 out of these 3 parameters)
Sec	condary	
•	To assess the efficacy of treatment with IV DNX twice daily given with oral	Time to Respiratory Response defined as meeting at least one criterion below
	oseltamivir compared to oral oseltamivir twice daily on time to respiratory response (TTRR)	Return to pre-morbid oxygen requirement (subjects with chronic oxygen use), OR
		Return to no requirement of supplemental oxygen, OR
		Respiratory rate ≤24/min (without supplemental oxygen)
•	To evaluate clinical measures of influenza illness following treatment with IV DNX twice daily given with oral oseltamivir compared to oral oseltamivir twice daily	Time to absence of fever
		Time to improved oxygen status
		Time to improved heart rate
		Time to improved SBP
		Proportion of subjects with clinical response over time
		Proportion of subjects with improved respiratory status over time
		Time to improvement of ventilation status: modality, frequencies and durations of invasive and non-invasive ventilator support, duration of oxygen supplementation.
		Length of stay in the ICU
		Frequency of ICU admission and readmission
		Length of stay in the hospital
		Rates of development of septic shock
		Frequency of antibiotic use

	Objectives	Endpoints
		Proportion of subjects with improvement in Ordinal scale of clinical efficacy over time: Death Mechanical vent In the ICU/ non MV Non-ICU hospitalization Hospital discharge
•	To characterize the safety and tolerability of IV DNX twice daily given with oral oseltamivir compared to oral oseltamivir twice daily	Frequency of adverse events (AEs) and serious adverse events (SAEs) Frequency of adverse events of special interest (AESIs) Change from baseline in clinical laboratory
•	To characterize the pharmacokinetics of IV DNX in subjects hospitalized for influenza	evaluations, and ECG parameters Standard pharmacokinetic parameters for IV DNX (i.e. AUC, Cmax, Cavg).
Ex	ploratory	
•	To assess changes in influenza viral load from nasopharyngeal swabs following treatment with IV DNX twice daily given with oral oseltamivir compared to oral OSV twice daily; perform resistance analysis and a multiplex PCR assay with respiratory virus panel to assess coinfection.	Change in quantitative influenza viral load over time and change from baseline measured from nasopharyngeal swab samples as determined by qRT-PCR and quantitative virus culture (qVC) Percentage of subjects with no detectable influenza viral RNA by qRT-PCR and qVC. Percentage of subjects with co-infected viruses by multiplex RT PCR. Percentage by type of co-infected viruses by multiplex RT PCR. Change in quantitative viral load of other virus co-infections over time and change from baseline measured from nasopharyngeal swab samples, as determined by qRT-PCR. Frequency of emergent resistance to OSV
•	To explore the effects of IV DNX twice daily given with oral oseltamivir compared to oral OSV twice daily with IV DNX placebo on biomarkers of inflammation and immune response from nasal samples or fluid, endotracheal samples, whole blood, bronchoalveolar lavage, and/or serum.	Quantitative and qualitative changes in exploratory biomarkers (may include but are not limited to: IL-8, procalcitonin, respiratory neutrophil cell counts, neutrophil elastase, and myeloperoxidase).
•	To characterize the PK response	PK exposure for DNX and pharmacodynamic

Objectives	Endpoints
relationship of IV DNX.	parameters.
To determine health outcome impact of IV	FLU PRO questionnaire
DNX twice daily given with oral OSV compared to oral OSV twice daily	Activities of daily living (Katz ADL Score)
compared to oral OSV twice daily	Activity level
	Hospital readmission rates

2.3. Study Design

Subjects meeting all eligibility criteria will be randomized 2:2:1 to one of three treatment groups in accordance with the central randomization schedule generated by Clinical Statistics prior to the start of the study, using validated internal software. All randomized subjects will take investigational drug or matching placebo twice daily for up to 5 days in the hospital.

2.4. Statistical Hypotheses

No statistical hypotheses will be formally tested.

3. PLANNED ANALYSES

3.1. Interim Analyses

An Independent Data Monitoring Committee (IDMC) will perform monitoring and reviews of available safety and efficacy data. Details are specified in the IDMC charter. No formal interim analysis will be performed.

3.2. Final Analyses

The final planned primary analyses will be performed after the completion of the following sequential steps:

- 1. All subjects enrol in the study at the time of study termination have completed the study, which is defined as completing the Day 45 assessment.
- 2. All required database cleaning activities have been completed and final database release and database freeze has been declared by Data Management.
- 3. All criteria for unblinding the randomisation codes have been met.
- 4. Randomisation codes have been distributed according to Ramos NG procedures.

4. ANALYSIS POPULATIONS

Table 1 Analysis Populations

Population	Definition / Criteria	Analyses Evaluated
Intent to Treat Exposed Population (ITT- E)	Comprised of all randomized subjects who receive at least one dose of investigational product. Subjects will be assessed according to their randomized treatment, regardless of the treatment they receive.	Study Population and disposition
Safety	 Comprised of all randomized subjects who receive at least one dose of IP. This population will be based on the treatment the subject actually received. 	Safety
Influenza Positive Population (IPP)	Comprised of all subjects in the ITT-E population with influenza infection (positive influenza PCR or culture at any timepoint) confirmed by central lab testing.	Efficacy, Health Outcomes, Virology, Biomarker
PK	Comprised of all subjects who underwent blood PK sampling during the study and from whom one or more blood concentration is determined.	• PK
All Subjects Screened	Comprised of all subjects screened for inclusion in the study	Study Population

NOTES:

Please refer to Appendix 13: List of Data Displays which details the population to be used for each display being generated.

4.1. Protocol Deviations

Important protocol deviations (including deviations related to study inclusion/exclusion criteria, conduct of the trial, patient management or patient assessment) will be listed.

Protocol deviations will be tracked by the study team throughout the conduct of the study in accordance with the Protocol Deviation Management Plan.

- Data will be reviewed prior to unblinding and freezing the database to ensure all important deviations are captured and categorised on the protocol deviations dataset.
- This dataset will be the basis for the summaries and listings of protocol deviations.

A separate listing of all inclusion/exclusion criteria deviations will also be provided. This listing will be based on data as recorded on the inclusion/exclusion page of the eCRF.

5. CONSIDERATIONS FOR DATA ANALYSES AND DATA HANDLING CONVENTIONS

Table 2 provides an overview of appendices within the RAP for outlining general considerations for data analyses and data handling conventions.

Table 2 Overview of Appendices

Section	Component
11.1	Appendix 1: Protocol Deviation Management and Definitions for Per Protocol Population
11.2	Appendix 2: Time & Events
11.3	Appendix 3: Assessment Windows
11.4	Appendix 4: Treatment States and Phases
11.5	Appendix 5: Data Display Standards & Handling Conventions
11.6	Appendix 6: Derived and Transformed Data
11.7	Appendix 7: Premature Withdrawals & Handling of Missing Data
11.8	Appendix 8: Values of Potential Clinical Importance
11.9	Appendix 9: Examination of Covariates, Subgroups & Other Strata
11.10	Appendix 10: Multiple Comparisons & Multiplicity
11.11	Appendix 11: Model Checking and Diagnostics for Statistical Analyses.
11.12	Appendix 12: Abbreviations and Trade Marks
Error!	Appendix 13: List of Data Displays
Referen ce	
source	
not	
found.	
11.14	Appendix 14: example Mock Shells for Data Displays

6. STUDY POPULATION ANALYSES

6.1. Overview of Planned Study Population Analyses

The study population analyses will be based on the ITT-E population, unless otherwise specified.

Table 3 provides an overview of the planned study population analyses, with full details of data displays being presented in Appendix 13: List of Data Displays.

 Table 3
 Overview of Planned Study Population Analyses

Endpoint / Parameter / Display Type	Data Displays Generate				
	Table	Figure	Listing		
Subject Disposition					
Subject Disposition	Υ[1]				
Reasons for Screen Failure			Y		
Reasons for Study Withdrawal	Y [2]		Υ		
Reasons for Discontinuation of Study Treatment	Υ		Υ		
Subjects for Whom the Treatment Blind was Broken			Y		
Planned and Actual Treatments			Υ		
Protocol Deviations					
Important Protocol Deviations			Υ		
Subjects with Inclusion/Exclusion Criteria Deviations			Y [3]		
Populations Analysed					
Study Populations	Υ				
Subjects Excluded from Any Population			Υ		
Demographic and Baseline Characteristics					
Demographic Characteristics	Y [1]		Υ		
Race and Racial Combinations	Υ		Y [4]		
Prior and Concomitant Medications					
Concomitant Medications			Υ		
Prior Exposure to Oseltamivir			Υ		
Exposure					
Exposure to Study Treatment	Υ		Υ		
Other					
Flu Details (includes influenza subtypes)	Y [1]		Υ		
Past and Current Medical Conditions	Υ		Υ		
Chronic underlying illness at baseline for Subjects with Renal Impairment			Y [5]		
Ventilation and Oxygenation Status at Baseline and Any Time	Y		Y		
Chest X-ray at Baseline			Υ		

CONFIDENTIAL

201023

Endpoint / Parameter / Display Type	Data Displays Generated				
	Table	Table Figure			

NOTES:

- Y = Yes display generated.
 [1] For ITT-E and IPP
 [2] Included in the Summary of Subject Disposition
 [3] Listing also includes analysis population exclusions.
 [4] Listing of race
 [5] Panel impointment
- [5] Renal impairment is based on Creatinine Clearance Criteria .

7. PRIMARY STATISTICAL ANALYSES

7.1. Efficacy Analyses

The primary efficacy analyses will be based on the IPP population, unless otherwise specified. Table 5 provides an overview of the planned efficacy analyses, with full details of data displays being presented in Appendix 13: List of Data Displays.

7.1.1. Overview of Planned Efficacy Analyses

Table 4 Overview of Planned Primary Efficacy Analyses

Endpoint	Stats Analysis			Summary		Indiv	idual
1	Т	F	L	Т	F	F	L
	Absolute						
Time to Clinical Response (TTCR)				Y [1]			Υ
Proportion of Subjects Achieving Improved Clinical				Y [1]			
Response by End of Study							

NOTES:

- T = Table, F = Figure, L = Listing, Y = Yes display generated.
- Stats Analysis = Represents TFL related to any formal statistical analyses (i.e. modelling) conducted.
- Summary = Represents TFL related to any summaries (i.e. descriptive statistics) of the observed raw data.
- Individual = Represents FL related to any displays of individual subject observed raw data
- [1]. Proportion of clinical response and Kaplan Meier estimates for the median of TTCR for each treatment group and 95% CI will be provided

7.1.2. Planned Efficacy Statistical Analyses

The clinical response is defined as hospital discharge due to clinical improvement or meeting following vital signs/ventilation criteria.

Sign of clinical response	Response criteria
Temperature ¹	≤36.6°C (≤97.9°F) – axilla/temporal, or
	≤37.2°C (≤99°F) – oral, or
	≤37.7°C (≤99.9°F) – rectal/core ⁵ , tympanic
AND	
Oxygen saturation ^{2,3}	≥95% (without supplemental oxygen)
AND 2 out of the following	ng 3 criteria:
Respiratory status	For subjects with chronic hypoxia and supplemental oxygen use: return to pre-morbid oxygen requirement, OR
	For subject with supplemental oxygen use at study entry: need for supplemental oxygen (administered by any modality – ventilator, non-invasive ventilation, facemask, face-tent, nasal canula, etc) to no need for supplemental oxygen, OR
	• For subject without supplemental oxygen use and respiratory rate > 24/min at study entry: respiratory rate ≤24/min
Heart rate	≤100/min
Systolic blood pressure ⁴	≥90 mmHg

- 1. Without the use of antipyretics within 8 hours
- 2. A subject with a history of chronic hypoxia (without supplemental oxygen) will satisfy normalization criteria for oxygen saturation if the value (without supplemental oxygen) is ≤2% from subject's historical oxygen saturation baseline as recorded within 12 months prior to enrolment as documented in the subject's medical records.
- 3. This requirement will be waived for subjects with a history of chronic supplemental oxygen requirement who have a baseline oxygen saturation <95% with supplemental oxygen, within 12 months prior to enrolment as documented in the subject's medical records.
- 4. Without inotropic support administered within 2 hours.
- 5. Core temperatures include rectal, indwelling catheters and Swan Ganz catheters.

Statistical Analyses

Endpoint(s)

• Time to Clinical Response (TTCR), days.

Derivation of TTCR

The clinical response based on vital signs/ventilation status requires 24-hour confirmation. Considering 2-hour assessment window, the response confirmation period is 22 hours, i.e. all assessments within 22 hours of the initial response and at least one at or beyond 22 hours need to meet the criteria in order for the response to be confirmed. Any missing scheduled assessment will be imputed with response value of 0 (1 means response). Only hospital discharge due to clinical response or a confirmed response based on vital signs/ventilation criteria is considered as event for the TTCR analysis. Hospital discharge due to clinical improvement can serve as 24-hour confirmation for the clinical response and the event date should be the onset of the vital signs response. Subjects who died prior to achieving a clinical response will be assigned a worst value of TTCR (99 days). All other subjects who did not achieve a confirmed response will be censored at the last assessment date of vital signs.

For further details of the calculation of TTCR see Section 11.6.4.

Model Specification

Not applicable

Model Checking & Diagnostics

Not applicable

Model Results Presentation

Not applicable

Sensitivity and Supportive Statistical Analyses

 No sensitivity analyses or subgroup analyses will be performed given the small number of subjects.

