5.1. Inclusion Criteria

A subject will be eligible for inclusion in this study only if all of the following criteria apply:

AGE
1. Adults 18 years (as per local laws) of age and older at the time of signing the informed consent.
TYPE OF SUBJECT AND DIAGNOSIS INCLUDING DISEASE SEVERITY

2. Presence of fever ($\geq 38.0^{\circ}\text{C}$ [$\geq 100.4^{\circ}\text{F}$] by any route) at Baseline (enrollment) or history of fever/feverishness during the 48 hours prior.
 
3. O_2 saturation $< 95\%$ on room air by trans-cutaneous method OR need for any supplemental oxygenation (non-invasive ventilation, facemask, facetent, nasal canula, etc) or ventilator support (mechanical ventilation, bi-level positive airway pressure [BIPAP], continuous positive airway pressure [CPAP]) or increase in oxygen supplementation requirement of ≥ 2 liters for subjects with chronic oxygen dependency. For those subjects with a history of chronic hypoxia (without supplemental oxygen), an oxygen saturation of at least 3% below the subject's historical baseline oxygen saturation.
 
AND AT LEAST 2 out of the following 3:
 
 • Respiratory rate > 24 breaths per minute. For those subjects who require ventilator support or oxygen supplementation, this requirement is waived. • Heart rate > 100 bpm • Systolic bp < 90 mm Hg. 
4. Severity of symptoms at enrollment:
 
 • Less severe hospitalized subjects are those who (but not limited to): 
 • are hemodynamically stable; • may require oxygenation with facemask, facetent, nasal canula, etc; • may or may not have radiological signs of lower respiratory tract disease; or • have exacerbation of underlying chronic disease, including asthma, chronic

obstructive pulmonary disease (COPD), or other cardiovascular conditions not leading to hemodynamic compromise.

- Critically ill hospitalized subjects are those who (but not limited to):
 - require CPAP, BIPAP, mechanical ventilation;
 - have hemodynamic instability (with or without pressor support); or
 - have central nervous system involvement (eg encephalopathy, encephalitis).
- 5. Presence of influenza that in the Investigator's judgment requires hospitalization for treatment and supportive care

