7.3.1. Primary Endpoint

The primary endpoint is time to clinical response (TTCR) ([Table 5](#)).

Clinical response is defined as resolution of at least 4 of the 5 signs described below within the respective resolution criteria, maintained for at least 24 hours, or hospital discharge, whichever comes first.

Table 5 Criteria for Time to Clinical Response

Sign of clinical response	Response criteria
Hospital discharge	Subjects who are discharged from hospital will be considered to have met the clinical response endpoint at the time of hospital discharge and are not required to have documented resolution of at least 4 response criteria (i.e. achieved success at the time of discharge if not observed prior to it).
OR	
Temperature ¹	≤36.6°C (≤97.9°F) – axilla, or ≤37.2°C (≤99°F) – oral, or ≤37.7°C (≤99.9°F) – rectal/core ⁵ , tympanic
AND	
Oxygen saturation ^{2,3}	≥95% (without supplemental oxygen)
AND 2 out of the following 3 criteria:	
Respiratory status	
 Return to pre-morbid oxygen requirement (subjects with chronic oxygen use), OR Need for supplemental oxygen (administered by any modality – ventilator, non-invasive ventilation, facemask, facemask, nasal canula, etc) to no need for supplemental oxygen, OR Respiratory rate ≤24/min (without supplemental oxygen)
Heart rate	≤100/min
Systolic blood pressure ⁴	≥90 mmHg

- Without the use of antipyretics within 8 hours
- A subject with a history of chronic hypoxia (without supplemental oxygen) will satisfy normalization criteria for oxygen saturation if the value (without supplemental oxygen) is ≤2% from subject's historical oxygen saturation baseline as recorded within 12 months prior to enrolment as documented in the subject's medical records.
- This requirement will be waived for subjects with a history of chronic supplemental oxygen requirement who have a baseline oxygen saturation <95% with supplemental oxygen, within 12 months prior to enrolment as documented in the subject's medical records.
- Without inotropic support administered within 2 hours.
- Core temperatures include measurements via a temporal artery thermometer, indwelling catheters and Swan Ganz catheters.

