11.6.4. Efficacy

Time to Clinical Response (TTCR)

TTCR will be derived as detailed in Section 7.1.2 The following is further considerations for the derivation of TTCR

- If an assessment time is missing the following times will be used in the calculation of TTCR: 8:00, 14:00, 20:00 respectively for morning, afternoon and evening assessments. The imputation will not be done for the study day 1.
- If the subject was discharged but is missing the date of discharge then the latest day from individual components will be used. If subject was discharged but the time of discharge is missing, 12:00 time will be used.
- If the subject withdraws consent on the same day as hospital discharge, TTCR will not be considered a failure.

- Deaths which occur after clinical response will not be considered a failure
- When a subject met vital sign criteria and was discharged from hospital during the 24 hour period of stability confirmation, the time of achieving TTCR was defined as the initial time at which vital signs were resolved and not the time of hospital discharge.
- If the clinical response has not been achieved by study completion, TTCR will be censored at the last assessment date of vital signs.
- If the subject did not achieve a clinical response the reason for censoring will be summarized (i.e. did not achieve vital sign resolution or reason for prematurely discontinuing the study).

Time to Respiratory Response (TTRR)

- Time to Respiratory Response defined as the first time meeting below, for at least 24 hours:
 - o Return to pre-morbid oxygen requirement (subjects with chronic oxygen use), OR
 - Need for supplemental oxygen (administered by any modality ventilator, noninvasive ventilation, facemask, facetent, nasal canula, etc) to no need for supplemental oxygen, OR
 - Respiratory rate >24/min and no supplement oxygen at baseline, and post baseline respiratory rate ≤24/min (without supplemental oxygen)
- Subjects who meet the above criteria at baseline (i.e., normal respiratory response) will not be included in the Kaplan Meier analysis and these subject not be considered as "improved" in the response rate
- If the symptoms have not resolved at Day 45, it will be censored at Day 45.

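### SAP 7.1.2 narrows the protocol's respiratory item without declaring it: a subject on room air with a rate of 24 or less at study entry cannot score it, and SAP 11.6.4 leaves the same subject's TTRR handling unclear

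*SAP*

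**What the plan says.** Protocol 7.3.1 (Table 5) requires temperature, oxygen saturation and two of three further items: respiratory status, heart rate and systolic pressure. One way to meet respiratory status is "Respiratory rate ≤24/min (without supplemental oxygen"). Nothing in that line depends on how the subject entered.

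SAP 7.1.2 keeps the two-of-three rule but conditions every respiratory row:
- The first row is open only to chronically hypoxic subjects who use oxygen, and is met when they are back at their pre-morbid level.
- The second row is open only to those on oxygen when they enter: "For subject with supplemental oxygen use at study entry: need for supplemental oxygen" must have ended.
- The third row covers a limited group on room air: "For subject without supplemental oxygen use and respiratory rate > 24/min at study entry: respiratory rate ≤24/min"

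For TTRR, SAP 11.6.4 writes the third criterion as "Respiratory rate >24/min and no supplement oxygen at baseline, and post baseline respiratory rate ≤24/min (without supplemental oxygen"). It then says of subjects who meet the criteria at baseline, which it explains as being normal already, that they "will not be included in the Kaplan Meier analysis and these subject not be considered as" having improved when the rate is computed.

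SAP 2.1, the section for changes to the protocol-defined analysis, reports the early termination, the absence of formal testing and a reduced set of outputs. It does not mention a changed respiratory criterion.

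**The concern.** The three SAP rows do not cover every eligible subject. Someone who is not on oxygen and already breathes at 24/min or less at entry has no row under which the respiratory item can be met, although Table 5 would grant it at once. For that subject the two-of-three rule in the primary endpoint becomes a requirement for both heart rate and systolic pressure. In the key secondary endpoint the same state is described as normal. The primary endpoint is therefore derived by a stricter rule than the protocol's for one kind of subject, the change is not announced, and the two respiratory definitions in the SAP do not fit together. TTCR and TTRR are the only time-to-event efficacy endpoints that this SAP summarises.

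**Working it through.** No power or error-rate figure depends on this rule, so the check sets the passages side by side.

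**Step 1. Can such a subject be enrolled?** Protocol 5.1, criterion 3, accepts saturation below 95% "on room air by trans-cutaneous method OR need for any supplemental oxygenation", so oxygen use is not compulsory. It adds "AND AT LEAST 2 out of the following 3": rate >24, heart rate >100, systolic pressure <90. Three yes/no signs give 2 × 2 × 2 = 8 patterns, of which four have at least two signs present. Exactly one of those four has a rate of 24 or less: heart rate >100 with systolic pressure <90. That pattern on room air is eligible and falls outside all three SAP rows.

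**Step 2. What changes for that subject in TTCR?** Take temperature and saturation as met, with the subject still on room air at 24/min or less.

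| Heart rate ≤100 | Systolic ≥90 | Protocol Table 5 | SAP 7.1.2 |
|---|---|---|---|
| yes | yes | response | response |
| yes | no | response | no response |
| no | yes | response | no response |
| no | no | no response | no response |

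The protocol gives a response in 3 of 4 states and the SAP in 1 of 4. These are counts of states, not probabilities. If the subject's rate later exceeds 24, both rules need heart rate and systolic pressure, and they agree. For subjects entering on room air with a rate above 24, the rules agree in every state. For subjects on oxygen at entry, both documents give credit for coming off oxygen.

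**Step 3. A second way into the gap.** The SAP does not define 'study entry'. SAP 11.5.2.1 takes baseline as the latest pre-dose value. Suppose a subject qualifies with rate >24 and heart rate >100, has systolic pressure ≥90, and the rate settles to 24 or less before dosing. If 'study entry' means baseline, the subject is in the gap. Under Table 5, respiratory status plus systolic pressure already make two of three; under the SAP, heart rate must also normalise. A need for oxygen that ends before the last pre-dose reading has the same effect. This route does not require hypotension.

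**Step 4. TTRR.** Two readings of SAP 11.6.4 are possible.
- By its explanatory phrase, the subject is normal at baseline, is left out of the Kaplan-Meier analysis and is not counted as improved. The denominator of the response rate is not stated.
- By its literal criteria, the third one requires a rate above 24 at baseline, so a room-air subject at 24 or less does not meet the criteria at baseline and is not excluded. Unless oxygen is started later and then stopped, that subject has no route to an event and is censored at Day 45.

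The programming note to Figure 2.2 (SAP 11.13.6) provides for subjects who resolved before baseline, which suggests that the first reading is intended.

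**The case against.** The strongest reply is that the group may be empty. Direct entry needs heart rate >100 together with systolic pressure <90. Protocol 4.3 places hemodynamic instability with the critically ill, and protocol 4.1.2 holds back their enrolment until about 30 less severe subjects have been reviewed. The study stopped at 10. This stands for the direct route, with the caveat that the protocol gives no numeric cut-off for instability. It does not close the route in step 3, which is open to less severe subjects.

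A second reply is that nothing is tested. The SAP calls its analyses descriptive, lists TTCR, TTRR and vital signs by subject, and plots each subject, so a reader could re-score either endpoint. That limits the consequence, but the summary tables would still follow a rule that differs from the protocol's.

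A third reply is that leaving subjects who cannot improve out of a time-to-improvement curve is defensible. It is; the defect is that the set is unclear and the rate's denominator is not given.

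A reader might also infer that the subject is scored as never normal in the primary endpoint. The text does not support that: only one of three interchangeable items is out of reach, and heart rate plus systolic pressure, or discharge for improvement, still gives a response. Nor does SAP 11.6.4 say that the subject stays in the response-rate denominator as a failure. The influenza-positive population is the default for secondary efficacy (SAP 8.1.1), so that reading is possible, but it is an inference.

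**Conclusion.** The point holds as a definite but small inconsistency. SAP 7.1.2 is stricter than Table 5 for subjects on room air with a rate of 24 or less at study entry, the change is undeclared, and SAP 11.6.4 does not settle how the same subjects enter TTRR.

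The number affected is not in the documents. It lies somewhere from 0 to 10 and may well be zero. It depends on what 'study entry' means and on how many subjects improved between eligibility and the last pre-dose value.

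No size of effect can be given. One might model the delay as waiting for the later rather than the earlier of heart rate and systolic pressure. TTCR also needs temperature, saturation and 24-hour confirmation, and discharge can end it sooner, so the delay could be nil. One might also say that a single subject moves an arm's respiratory response rate by 25 points (1/4) or 50 points (1/2). That assumes an exact 4:4:2 split of the 10, all of them in the influenza-positive population, and a denominator that the SAP does not state.

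**What to change.** In SAP 7.1.2, restore the Table 5 wording for the third row: respiratory rate ≤24/min without supplemental oxygen, whatever the rate at entry. Define 'study entry', saying whether it is the eligibility reading or the last pre-dose value.

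In SAP 11.6.4, define normal at baseline as not on new supplemental oxygen with a rate ≤24/min. Use the same set of subjects for the Kaplan-Meier analysis and for the response-rate denominator, and footnote the number excluded.

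The cost is a few sentences in the SAP and a small change to two derivations. No new data are needed, since vital signs and oxygen status are already collected and listed. The change belongs before unblinding, when the SAP synopsis says decisions about the final analysis are made.
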